HYPOTHESIS

In our study we hypothesize that sub-dissociative-dose ketamine administered as a single agent via breath actuated nebulizer at the dose of 1.5 mg/kg will provide better analgesia at 30 min

post-administration with similar rates of side effects in comparison to 0.75 mg/kg and 1 mg/kg for ED patients presenting to the ED with acute and chronic painful conditions. The primary outcome of this trial is the comparative reduction in participant's pain scores at 30 minutes post medication administration.

STUDY DESIGN

Subjects: Patients 18 years of age and older presenting to the ED with acute and chronic painful conditions such as traumatic and non-traumatic abdominal, flank, back, or musculoskeletal pain as well as exacerbation of chronic abdominal, musculoskeletal and neuropathic pain with a score of 5 or more on a standard 11- point (0 to 10) numeric rating scale and requiring sub-dissociative dose ketamine analgesia, as determined by the treating attending physician. Patients' screening and enrollment will be performed by study investigators and research assistants. All patients will be enrolled at various times of the day when study investigators will be available for patient enrollment and an ED pharmacist will be available for medication preparation

Eligibility Criteria: Patients 18 years of age and older presenting to the ED with acute and chronic painful conditions such as traumatic and non-traumatic abdominal, flank, back, or musculoskeletal pain as well as exacerbation of chronic abdominal, musculoskeletal and neuropathic pain with a score of 5 or more on a standard 11- point (0 to 10) numeric rating scale.

Exclusion Criteria: Altered mental status, allergy to ketamine, pregnant patients, weight greater than 150 kg, unstable vital signs (systolic blood pressure <90 or >180 mm Hg, pulse rate <50 or >150 beats/min, and respiration rate <10 or >30 breaths/min), inability to provide consent, and past medical history of alcohol or drug abuse, or schizophrenia.

Design: This is a prospective, randomized, double-blind trial comparing analgesic efficacy and safety of nebulized SDK administered at three different doses to patients presenting to the ED of Maimonides Medical Center with acute and chronic painful conditions. Upon meeting the eligibility criteria, patients will be randomized into one of three study arms based on the dosing of the SDK: 0.75 mg/kg, 1 mg/kg, and 1.5 mg/kg.

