Data Analysis: Data analyses will include frequency distributions, paired t-test to assess a difference in pain scores within each group, and independent-sample t-test to assess differences in pain scores between the 3 groups at the various intervals.

Mixed-model linear regression will be used to compare changes in pain numeric rating scale across time points. This will compensate for participants lost to follow-up and allow all patients' data to be analyzed on an intention-to-treat principle.

For categorical outcomes (eg, complete resolution of pain), a X^2 or Fisher's exact test will be used to compare outcomes at 30 minutes. Percentage differences and 95% confidence intervals between the treatment groups will be calculated for all time points with $P < .05$ to denote statistical significance. Based on the validation of a verbally administered rating scale of acute pain in the ED and the comparison of verbal and visual pain scales, we will use a primary outcome consisting of a minimal clinically meaningful difference of 1.3 between three groups at the 30-minute pain assessment.^{28,29}

Sample Size: Assuming an SD of 3.0, a power analysis determined that a repeated-measures ANOVA with a sample size of 34 patients per group (102 total) will provide at least 80% power to detect a difference of at least 1.3 at 30 minutes (as well as at any other interval post-baseline), with an $\alpha = .05$. To account for possible missing data the total sample size will be 120 patients

(40 per group). A pre-planned interim data analysis will occur upon reaching a total of total of 60 patients (20) patients per group.

Expected Outcomes: The primary outcome will include a comparative reduction of pain scores on numeric rating pain scale (NRS) between recipients of nebulized SDK at three different doses at 30 minutes post-analgesic administration.

ATTACHMENTS

List any attachments (contracts, participant materials, data collection tools, etc.)

Protocol for analgesic administration via Breath Actuated Nebulizer

MAIMONIDES MEDICAL CENTER DEPARTMENT OF EMERGENCY MEDICINE (ED)

Protocol for ED Analgesics Administration via Breath-Actuated Nebulizers (BAN)

Background

[figure not shown]

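### The plan names no deciding analysis for the 30-minute comparison and does not say whether 1.5 mg/kg must beat one or both lower doses; a false finding for 1.5 mg/kg has probability 4.5% or at most 2.5% accordingly

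*Combined protocol and SAP*

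**What the plan says.** All references are to the combined protocol and SAP.

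- **Hypothesis** (under that heading): nebulized ketamine "at the dose of 1.5 mg/kg will provide better analgesia at 30 min", "with similar rates of side effects in comparison to 0.75 mg/kg and 1 mg/kg". The same paragraph makes the reduction in pain score at 30 minutes the primary outcome. Expected Outcomes describes it as a comparison among the recipients of all three doses.
- **Between-dose tests** (Data Analysis): an "independent-sample t-test to assess differences in pain scores between the 3 groups at the various intervals". Separately, "Mixed-model linear regression will be used to compare changes in pain numeric rating scale across time points", which the plan justifies by loss to follow-up and intention-to-treat.
- **Level** (Data Analysis): percentage differences and confidence intervals "will be calculated for all time points with $P < .05$ to denote statistical significance". Sample Size also states an alpha of .05. No other level appears.
- **Effect of interest** (Data Analysis): "we will use a primary outcome consisting of a minimal clinically meaningful difference of 1.3 between three groups at the 30-minute pain assessment".
- **Sample Size**: with an SD of 3.0, "a repeated-measures ANOVA with a sample size of 34 patients per group (102 total) will provide at least 80% power" for a 1.3-point difference at 30 minutes. Enrolment is 120 patients, 40 per group. Also, "A pre-planned interim data analysis will occur upon reaching a total of total of 60 patients".

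**The concern.** A t-test compares two groups, so applying it to three groups most naturally means three pairwise tests at 30 minutes. The plan sets no overall test before them, no order, no adjustment, and no statement of which pairs must succeed. The mixed model is not called primary and has no stated 30-minute contrast. The ANOVA appears only in the power statement.

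The same data could therefore be reported as positive or negative, depending on which analysis is taken as deciding and on whether one contrast or two must be significant. If the looser reading were chosen after seeing the results, the chance of a false finding for 1.5 mg/kg would exceed the 2.5% expected in one direction.

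**Working it through.** **Inputs.** From the documents: three arms, 34 evaluable and 40 enrolled per arm, SD 3.0, difference 1.3, level .05. My assumptions: two-sided tests, the .05 level applied to each pairwise t-test, normal scores, complete data, the 30-minute time only, no interim look. Means below are points of benefit for 0.75, 1 and 1.5 mg/kg in that order.

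**1. The plan's own figure: at least 80% power at 34 per group.**

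One pair: standard error = 3.0 × √(2/34) = 0.728, and 1.3/0.728 = 1.79. The critical t on 66 df is 2.00, which gives 42% power. It is 48% at 40 per arm.

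Overall three-group F-test: noncentrality λ = n × Σ(mean − grand mean)² / 3.0².

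| Means | Σ of squares | λ, n = 34 | Power, n = 34 | λ, n = 40 | Power, n = 40 |
|---|---|---|---|---|---|
| 0, 0.65, 1.3 | 0.845 | 3.19 | 33% | 3.76 | 38% |
| 0, 0, 1.3 | 1.127 | 4.26 | 43% | 5.01 | 49% |
| 0, 1.3, 2.6 | 3.380 | 12.77 | 89% | 15.02 | 94% |

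The stated 80% is reached if neighbouring doses each differ by 1.3, or if an unstated correlation is assumed. For means 0, 0, 1.3 at 34 per arm, about 80% needs a correlation near 0.3 when five or six time points are averaged, or near 0.75 with baseline as a covariate.

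**2. False findings when all doses are equal.** The two 1.5 mg/kg contrasts share an arm, so their correlation is 0.5. Large-sample results:

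- Either contrast in favour of 1.5 mg/kg: 1 − Φ₂(1.96, 1.96; 0.5) = 4.54%.
- Both in favour: 2.5% + 2.5% − 4.54% = 0.46%.
- Any of the three pairs, either direction: 1 − studentized-range CDF at 1.96√2 for three groups = 12.2%.

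Simulating 1,000,000 trials with separate t-tests gives 4.5%, 0.5% and 12.2% at both 34 and 40 per arm. Rounding and clipping scores to 0–10 changes them by about 0.1 point at most.

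**3. Worst case for requiring both.** If 1.5 mg/kg is no better than at least one lower dose, that contrast alone favours it falsely at most 2.5% of the time, so both together cannot exceed 2.5%. With 1.5 equal to 1 mg/kg and both better than 0.75 mg/kg, simulation at 40 per arm gives 2.2% for a gap of 1.3 and 2.5% for a gap of 3.

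**4. Does the 1.3-point sentence supply the missing rule?** It does not say which pairs count, or whether 1.3 must be observed. At 40 per arm the smallest significant difference is 1.99 × 3.0 × √(2/40) = 1.34. Also requiring an observed 1.3 therefore lowers 12.2% only to 10.8%, and 4.5% to 4.0%. An observed 1.3 with no test gives 12.8% and 4.8%.

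**5. How often the missing rule changes the result.** With a true 1.3-point benefit over both lower doses and 40 per arm, exactly one of the two contrasts is significant in favour of 1.5 mg/kg in 33% of simulated trials. Those trials are positive if one contrast suffices and negative if both are needed.

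**6. Power if both contrasts must be significant in favour of 1.5 mg/kg** (SD 3.0, no correlation, simulated).

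| Means | n = 34 | n = 40 |
|---|---|---|
| 0, 0.65, 1.3 | 10% | 12% |
| 0, 0, 1.3 | 26% | 31% |
| 0, 1.3, 2.6 | 42% | 48% |

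**The case against.** The strongest reply is that the hypothesis already answers the question. It sets 1.5 mg/kg against 0.75 and 1 mg/kg together, which reads most naturally as better than both. On that reading the false-claim rate is at most 2.5% and no adjustment is needed. This stands as a reading, and it is why 12.2% should not lead the criticism: that figure also counts 0.75 against 1 mg/kg and results unfavourable to 1.5 mg/kg. But the hypothesis is not written as a success rule, and Expected Outcomes describes a comparison among all three doses.

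It can also be said that pairwise testing at .05 is inferred. That is fair. The plan does not use the word pairwise, and its P < .05 sits in the sentence on percentage differences. No stricter level is stated anywhere, however.

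A reader might infer that the trial will run at a 12.2% error rate. The documents do not support that, because they do not say that any significant pair counts as success. A reader might also infer that 80% power is unattainable without a baseline correlation. That is not so for the overall test: means of 0, 1.3 and 2.6 give 89% at 34 per arm. The plan simply does not state that pattern.

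**Conclusion.** The concern holds as a gap in specification: there is no deciding 30-minute analysis and no rule on one contrast or both. The size that bears on the trial's own hypothesis is a false finding for 1.5 mg/kg in 4.5% of equal-dose trials if either contrast may count, against 0.5% if both are required (never above 2.5%). The 12.2% applies only if any pair may count.

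These rates assume pairwise t-tests at two-sided .05, complete data and no interim look. At a fixed P < .05 they do not depend on the SD and barely change between 34 and 40 per arm. They were computed with t- and F-tests, not with the mixed model itself.

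The power shortfall does not cause the gap, but it follows from closing it. The stated 80% does not hold for the both-contrasts rule under any of the three patterns examined without a correlation. Of those patterns, it holds for the overall test only where neighbouring doses each differ by 1.3. The alpha for the interim look is a separate matter and is not part of this conclusion.

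**What to change.** Before unblinding:

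1. Name the 30-minute dose contrasts from the planned mixed model (dose, time and their interaction) as the deciding analysis, and call the t-tests descriptive.
2. Declare the hypothesis supported only if 1.5 mg/kg is significantly better than both 0.75 and 1 mg/kg, each at two-sided .05. This needs no preceding overall test, order or adjustment.
3. If claims on single pairs are wanted, make them only after a significant overall three-group test at 30 minutes at .05. In simulation with equal doses this holds the any-pair error at 5.0%.
4. State that 1.3 points is the yardstick for interpreting estimates and their intervals, not a test.
5. Restate power for the chosen rule, giving the assumed mean pattern, whether SD 3.0 refers to scores or to change, and any baseline correlation relied on.

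**Cost.** Fixing the rule needs no extra patients. Under the both-contrasts rule, single-pair results become descriptive. The stated power becomes less favourable, and the sponsor must either accept the lower figure or justify the assumptions behind a higher one.

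### The plan does not say which between-group analysis decides the 30-minute primary outcome, and none is stated to adjust for the baseline pain score

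*Combined protocol and SAP*

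**What the plan says.** The combined protocol and SAP describes the primary outcome in three places. Hypothesis and Expected Outcomes both word it as a reduction; the latter begins "The primary outcome will include a comparative reduction of pain scores on numeric rating pain scale (NRS". Data Analysis words it differently: "we will use a primary outcome consisting of a minimal clinically meaningful difference of 1.3 between three groups at the 30-minute pain assessment".

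Three between-group methods could decide that outcome:

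- Data Analysis, t-tests on scores: "independent-sample t-test to assess differences in pain scores between the 3 groups at the various intervals".
- Data Analysis, mixed model on changes: "Mixed-model linear regression will be used to compare changes in pain numeric rating scale across time points". Of this model the plan adds: "This will compensate for participants lost to follow-up and allow all" patients to be analysed by intention to treat.
- Sample Size, a third method: "a power analysis determined that a repeated-measures ANOVA with a sample size of 34 patients per group".

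The only Data Analysis test tied to 30 minutes by name is for categorical outcomes, where a chi-square or Fisher's "exact test will be used to compare outcomes at 30 minutes".

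Baseline NRS is recorded on the 0 to 10 scale (Data Collection Procedures), and entry requires a score of 5 or more (Eligibility Criteria). No covariate is listed for any method. Hypothesis sets 1.5 mg/kg against each of the two lower doses. Sample Size also states: "A pre-planned interim data analysis will occur upon reaching a total of" 60 patients.

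**The concern.** No method is named as decisive, and the wording of the outcome does not match the wording of the tests: the outcome is a reduction, but the t-tests are on pain scores. The mixed model is on changes, but no 30-minute contrast is stated for it. The repeated-measures ANOVA gives effects for arm, time and their interaction, and no 30-minute comparison is specified from it either.

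Two choices stay open: score or change, and a three-group test or two contrasts (and, if two, whether both must succeed or one is enough). Either choice could be made after results are seen, including at the interim look. At stake are the error rate and the clarity of the primary conclusion, together with some precision if the raw-score t-test is the one used.

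**Working it through.** **The plan's own figure.** Inputs from Sample Size: difference 1.3, SD 3.0, α .05 (two-sided assumed), 80% power, 34 per group. For one pairwise comparison at 30 minutes, n = 2(1.96 + 0.84)² × 3.0² / 1.3² gives 84 per group. At 34 per group the t-test has 42% power. The stated 34 therefore does not reproduce as a 30-minute comparison. It can be reached with unstated inputs. One example is an ANOVA between-group test averaged over six time points with correlation 0.3 and means 0, 0, 1.3 (81% power), but that tests a time-averaged difference. The sample size statement therefore does not identify the 30-minute analysis.

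**Assumptions not in the documents.** Write s for the baseline SD and ρ for the correlation between baseline and 30-minute NRS. Equal counts at NRS 5 to 10 give s = √(35/12) = 1.71; I use s = 1.5 to 1.71 and ρ = 0.3 to 0.5. The planned 40 per arm and two-sided .05 are used throughout. The plan does not say whether 3.0 is the SD of the score or of the change, so both are shown. Power is from the noncentral t with 78 df.

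**If 3.0 is the SD of the score.** Change SD = √(9 + s² − 6ρs); adjusted SD = 3.0√(1 − ρ²). The unadjusted score has 48% power in every row.

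| s | ρ | change SD | power, change | adjusted SD | power, adjusted |
|---|---|---|---|---|---|
| 1.5 | 0.3 | 2.92 | 50% | 2.86 | 52% |
| 1.5 | 0.5 | 2.60 | 60% | 2.60 | 60% |
| 1.71 | 0.3 | 2.97 | 49% | 2.86 | 52% |
| 1.71 | 0.5 | 2.61 | 60% | 2.60 | 60% |

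The slope of the 30-minute score on baseline, ρ × 3.0/s, is 0.53 to 1.0 in these rows.

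**If 3.0 is the SD of the change.** Score SD = ρs + √(ρ²s² + 9 − s²); adjusted SD = score SD × √(1 − ρ²). The change analysis has 48% power in every row.

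| s | ρ | score SD | power, score | adjusted SD | power, adjusted |
|---|---|---|---|---|---|
| 1.5 | 0.3 | 3.09 | 46% | 2.95 | 50% |
| 1.5 | 0.5 | 3.45 | 38% | 2.99 | 48% |
| 1.71 | 0.3 | 3.03 | 47% | 2.89 | 51% |
| 1.71 | 0.5 | 3.46 | 38% | 3.00 | 48% |

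On this reading the slope at ρ = 0.5 is slightly above 1 (0.5 × 3.45/1.5 = 1.15 and 0.5 × 3.46/1.71 = 1.01).

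**Score against change on the same data.** 100,000 simulated two-arm trials per cell, normal scores, complete data, 3.0 as the SD of the score. With complete data, the 30-minute contrast of a saturated mixed model on changes equals the difference in mean change, so the change t-test stands in for it.

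| s | ρ | verdicts differ, true difference 1.3 | either significant, no difference |
|---|---|---|---|
| 1.5 | 0.3 | 16.5% | 7.3% |
| 1.5 | 0.5 | 19.1% | 7.2% |
| 1.71 | 0.3 | 18.6% | 7.6% |
| 1.71 | 0.5 | 21.2–21.5% (repeat runs) | 7.6% |

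**Why a baseline covariate removes that choice.** If change = a + arm effect + βb, where b is baseline, then score = a + arm effect + (β + 1)b. The arm effect and its standard error are the same. With a separate baseline slope at each time, this holds at 30 minutes.

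**The decision rule.** Take the unadjusted score, 3.0 as its SD, and 1.5 mg/kg better than both lower doses by 1.3. Power is 32% if both contrasts are required, 53% if either suffices under Holm, and 49% for a one-way three-group test. These figures show why the rule must be named; they do not measure the score-or-change problem.

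**The case against.** The best reply is that the mixed model is primary in all but name. It is the only method tied to intention to treat and to loss to follow-up, and it works on changes, which fits the two formal outcome statements. The 1.3-point sentence sets a threshold and a time and does not clearly select raw scores. Much of this stands: the mixed model is the natural candidate. But the text does not call it primary, gives no 30-minute contrast from it, and sizes the trial on a method with another name.

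A second reply is that leaving baseline out as a covariate is no error in a randomised trial, and that a change analysis already uses baseline. That also stands. Adjustment is worth having because it settles score against change and improves on the raw-score t-test, not because the plan is invalid without it.

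Third, the phrase about a difference between three groups, together with the ANOVA, supports a three-group primary test. That reading must stay open to the sponsor.

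A reader might infer larger effects from a stronger correlation: at ρ = 0.7, adjusted power is 76% and disagreement reaches about 30%. With a score SD of 3.0, that needs a baseline slope of 0.7 × 3.0/1.71 = 1.23 to 0.7 × 3.0/1.5 = 1.40, so that each extra baseline point predicts more than one extra point at 30 minutes. Entry at NRS 5 or more also restricts the baseline range, which tends to lower ρ. The documents give no correlation, so I do not rely on those figures.

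**Conclusion.** The point holds as a gap in specification. The plan does not say which between-group analysis decides the 30-minute outcome, none is stated to adjust for baseline NRS, and the choice between a three-group test and two contrasts is not settled.

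Under the assumptions above, with 3.0 as the score SD, the open choice between score and change alters the verdict in about 17–21% of trials when the true difference is 1.3. Choosing the significant one gives about 7–8% type I error on one contrast. Single-contrast power is 48% for the score, 49–60% for change and 52–60% adjusted if 3.0 is the score SD. It is 38–47%, 48% and 48–51% if 3.0 is the change SD. The gain from adjustment is therefore mainly over the raw-score t-test.

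A reader might infer that the planned comparisons are biased, or that adjustment would restore the stated 80% power. The documents support neither: allocation is randomised, and no adjusted figure in the tables above exceeds 60%. The shortfall of 34 per group against 80% is a separate issue. The absence of a named primary analysis can be read directly from the text; the sizes depend on an assumed correlation and baseline SD.

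**What to change.** Make the already planned mixed model the single primary analysis: NRS at 15, 30, 60, 90 and 120 minutes as outcome; baseline NRS (by time) as covariate; arm, time and arm-by-time; a stated covariance structure; all patients as randomised. Report its 30-minute arm contrasts with 95% confidence intervals, and make the t-tests descriptive.

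Before any data are seen, including at the interim look at 60 patients, state:

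- whether the primary test is the three-group test at 30 minutes or the two hypothesised contrasts and, if the contrasts, whether both are required (each at two-sided .05) or either suffices (Holm at an overall .05);
- whether the SD of 3.0 is of the score or of the change;
- the power of the chosen rule.

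The cost is SAP wording and possibly a less favourable stated power. No new data or patients are needed, since the baseline score, the five time points and the mixed model are already in the plan.

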Data Collection Procedures: Each patient will be approached by a study investigator for acquisition of written informed consent and Health Insurance Portability and Accountability Act authorization after being evaluated by the treating emergency physician and determined to meet study eligibility criteria. When English will not be the participant's primary language, a staff interpreter or licensed telephone interpreter would be used. Baseline pain score will be determined with an 11-point numeric rating scale (0 to 10), described to the patient as "no pain" being 0 and "the worst pain imaginable" being 10. A study investigator will record the patient's body weight and baseline vital signs. The on-duty ED pharmacist will prepare a breath-actuated nebulizer with doses of 0.75 mg/kg, 1 mg/kg, and 1.5 mg/kg according to the predetermined randomization list,

which will be created in SPSS (version 24; IBM Corp, Armonk, NY) with block randomization of every 10 participants. The medication will be delivered to the treating nurse in a blinded fashion and will be administered via breath-initiated nebulization with a minimum time of 5 min and maximum time of 15 min up to three doses.

Study investigators will record pain scores, vital signs, and adverse effects at 15, 30, 60, 90, and 120 minutes. If patients reported a pain numeric rating scale score of 5 or greater and requested additional pain relief, a second (equivalent to the first dose) of SDK via BAN will be administered to the patient in a blinded fashion. In situations when nebulized SDK will fail to achieve acceptable (by patient) pain relief or patient will refuse to continue nebulized SDK treatment, morphine at 0.1 mg/kg will be administered as a rescue analgesic.

All data will be recorded on data collection sheets, including patients' sex, demographics, medical history, and vital signs and entered into SPSS (version 24.0; IBM Corp) by the research manager. Development of the randomization list, confirmation of written consent acquisition for all participants, and statistical analyses will be conducted by the research manager and statistician, who would work independent of any data collection.

Patients will be closely monitored for any change in vital signs and for adverse effects during the entire study period (up to 2 h) by study investigators. Common adverse effects that are associated with sub-dissociative dose ketamine are feeling of unreality, dizziness, nausea, vomiting, and sedation.

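### The mixed model's protection against lost patients is stated without its condition, and it does not reach the between-arm t-tests named for 30 minutes

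*Combined protocol and SAP*

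**What the plan says.** The primary outcome, given under Hypothesis and again under Expected Outcomes, is at one time point: "The primary outcome of this trial is the comparative reduction in participant's pain scores at 30 minutes post medication administration". The Data Analysis section offers several methods that could bear on it:

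- Between-arm tests at each time: "independent-sample t-test to assess differences in pain scores between the 3 groups at the various intervals".
- A longitudinal model: "Mixed-model linear regression will be used to compare changes in pain numeric rating scale across time points". The next sentence gives its benefit: "This will compensate for participants lost to follow-up and allow all" patients to be analysed by intention to treat.
- For categorical outcomes such as complete resolution of pain: "a X^2 or Fisher's exact test will be used to compare outcomes at 30 minutes".

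The Sample Size section names a further method, repeated-measures ANOVA, and makes the only other provision for missing data: "To account for possible missing data the total sample size will be 120 patients", up from 102.

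The plan does not say which method is the primary 30-minute test. It gives no missing-data assumption, no rule for a patient without a 30-minute score, no definition of the analysis set and no sensitivity analysis. It also leaves open the model's covariance, its covariates, and whether baseline is an outcome or a covariate.

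**The concern.** A likelihood-based mixed model uses every recorded score from patients with incomplete follow-up. This removes bias from loss only when, given the recorded scores, the chance that a score is missing does not depend on its unseen value. The plan states the benefit and omits the condition.

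The t-tests have no such protection. A two-sample t-test at 30 minutes can use only patients who have a 30-minute score, unless a rule supplies one, and the plan has none. It makes no use of the baseline or 15-minute scores. Because no primary test is named, the headline dose comparison could come from the t-test while a reader takes the compensation and intention-to-treat wording to cover it.

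At stake is the dose comparison. If patients in more pain go unscored more often in one arm, that arm's 30-minute mean looks better than it is.

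**Working it through.** **1. The plan's own figure.** 34/(1 − 0.15) = 40 per group, and 102/120 = 0.85. The increase therefore implies a 15% allowance, 6 of 40 per arm, although no rate is stated. Whether 34 itself follows from the stated inputs is a separate question, and nothing here depends on it.

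**2. Inputs.** From the Sample Size section: SD 3.0, target difference 1.3, 40 per arm. Assumed: 15% missing at 30 minutes; correlation ρ between any two scores of one patient of 0.5 to 0.8; missingness that is random in one arm and, in the other, logistic in the patient's pain with log-odds 0.5 (mild), 1 (moderate) or 2 (strong) per SD. In the moderate case 4.5% are missing at 1 SD below the mean and 26% at 1 SD above.

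**3. t-test, loss driven by unseen 30-minute pain.** The bias of an observed-only mean is p/(1 − p) × d. Here p is the proportion missing and d is how much worse the missing patients are than their arm's mean. Integrating the logistic curve over a normal distribution with p = 0.15 gives d = 0.41, 0.75 and 1.15 SD, which times 3.0 is 1.23, 2.25 and 3.45 points. With 0.15/0.85 = 0.176:

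- mild: 0.176 × 1.23 = 0.22
- moderate: 0.176 × 2.25 = 0.40, which is 0.40/1.3 = 31% of the target
- strong: 0.176 × 3.45 = 0.61

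**4. t-test, loss driven by the recorded 15-minute score.** The bias is multiplied by ρ: from 0.5 × 0.22 = 0.11 to 0.8 × 0.61 = 0.49. Simulation gave 0.12 to 0.47.

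**5. Mixed model.** If loss depends on the recorded 15-minute score, the bias is zero in theory and near zero in simulation. If it depends on unseen pain, roughly (1 − R²) of the t-test bias remains, where R² is the share of 30-minute variance explained by the recorded scores. With baseline and 15 minutes recorded and a common ρ, R² = 2ρ²/(1 + ρ): 0.5/1.5 = 0.33 at ρ = 0.5, and 1.28/1.8 = 0.71 at ρ = 0.8. The bias therefore runs from about 0.29 × 0.22 = 0.06 to 0.67 × 0.61 = 0.41. Simulation gave 0.06 to 0.43.

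**6. Same loss in both arms.** Each arm's mean is shifted equally, so the contrast is not: 0.40 − 0.40 = 0 in the moderate case.

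| Loss at 30 minutes | t-test bias | Mixed-model bias |
|---|---|---|
| Same rate and same relation to pain in all arms | none | none |
| Differs by arm, depends on recorded pain | about 0.1–0.5 | near 0 |
| Differs by arm, depends on unseen pain | about 0.2–0.6 | about 0.1–0.4 |

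**7. Check with a different setup.** Two arms, true difference 1.30, six time points, ρ = 0.6, log-odds 1.5 per SD, dropouts missing from 30 minutes onward. Estimated differences, t-test / mixed model:

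- 15% loss, same mechanism in both arms: 1.27–1.32 / 1.28–1.32
- 15% loss, pain-related in one arm only: 1.62 / 1.30 (recorded pain); 1.82 / 1.60 (unseen pain)
- 25% against 5% loss, pain-related in both: 1.69 / 1.32 (recorded); 1.93 / 1.69 (unseen)

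**8. Ignoring baseline.** This costs precision even with no missing data. With baseline used, the residual SD is 3.0 × √(1 − ρ²): 2.60 at ρ = 0.5 and 1.80 at ρ = 0.8. At 34 per arm, two-sided power for 1.3 points is 43% for the plain t-test, against 54% and 85% with baseline adjustment at those correlations.

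**The case against.** Several points on the other side stand and limit what can be said.

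- **Scope of the sentence.** A reader might infer that the plan makes a false promise about its whole analysis. It does not. The compensation sentence follows the mixed model and refers to that model only. The model does use all recorded scores from incompletely followed patients. The fault is the missing condition and the reach of the benefit.
- **The primary result.** A reader might infer that the primary result will be an observed-cases test. The plan does not say so, because it names no primary test. The chi-square or Fisher test is for categorical outcomes, not the primary pain-score reduction.
- **Who goes unscored.** A reader might take "patient will refuse to continue nebulized SDK treatment" in Data Collection Procedures to mean that patients with poor relief go unscored. The passage is about refusing treatment and receiving rescue. Investigators are to record scores through 120 minutes and monitor patients for up to 2 hours, so loss by 30 minutes may be small.
- **Rate.** 15% is an implied overall allowance, not a 30-minute rate. At 5% missing, the moderate case driven by unseen pain in one arm gives a t-test bias of 0.14.
- **Asymmetry.** Nothing in the documents shows that loss will differ by arm in a double-blind comparison of doses of one drug. Without a difference there is no bias.
- **Later scores.** A patient who misses 30 minutes but is scored afterwards gives the model more information. In the moderate case with unseen pain, the model's bias is 0.15–0.31 using the 15-minute score alone and about 0.09–0.25 using baseline and all other times.

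The reply is narrower but holds. None of these points supplies the missing condition or a rule for the t-tests. Even where loss depends only on recorded pain, the setting that favours the plan's claim, the t-test can be biased and the mixed model is not.

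**Conclusion.** The concern holds in limited form. The compensation claim is valid only when missing scores depend on recorded scores, and it does not cover the between-arm t-tests at each interval, including 30 minutes. If loss differs by arm, the t-test bias could be about 0.1 to 0.5 points when loss follows recorded pain, where the mixed model has essentially none. It could be about 0.2 to 0.6 points when loss follows unseen pain, where the model keeps about 0.1 to 0.4. Against the 1.3-point target, 0.6 is 46% (0.6/1.3). If loss is the same in all arms, neither method is biased.

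The documents give the SD and the increase from 34 to 40. The 15% rate at 30 minutes, the correlation and the missingness patterns are assumptions, so the figures show what could happen, not what is expected. The case for change does not rest on them alone: the mixed model is already planned, uses data already collected, and makes better use of baseline.

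**What to change.** - **Replace the between-arm interval t-tests** with arm contrasts at each time from one mixed model: categorical time, arm by time, and baseline NRS in the response vector, with the baseline mean held common across arms, as randomization justifies. Every randomized patient with a baseline score then enters the model, although one with only a baseline score adds almost nothing to the 30-minute contrast.
- **Name the model's 30-minute arm contrast** as the primary test.
- **Replace the compensation wording** with a statement that the analysis is valid if missing scores depend only on recorded scores.
- **Optional:** one delta-shift sensitivity analysis, worsening missing 30-minute scores separately by arm and reporting the shift at which the conclusion changes. The model cannot test its own assumption.

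Counting a missing score as pain not resolved in the categorical analysis should not be required. It is one convention among several and can itself bias the comparison if missingness differs by arm. If used, present it as a sensitivity analysis. These changes also do not settle how scores after rescue or refusal are used, on which the plan is silent.

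The cost is plan wording and slightly more analysis work, with no added patients, assessments or data. The change is most credible if made before anyone sees unblinded results, including the planned interim analysis at 60 patients.
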